8.3 Study procedures

- The Clavien Dindo classification is correlated with the complexity of the operation as well as the length of hospitalization and may be used internationally as quality screening for surgery^{81,82}. The Comprehensive Complication Index summarizes the postoperative wellbeing of the patient concerning complications based on the Clavien-Dindo classification⁸³. The CCI-score is easily assessed at www.assesssurgery.com. Both scores will be determined at four weeks after surgery.
- The 6MWT evaluates the ability of an individual to maintain a moderate level of physical activity over a time period reflective of the activities of daily living.⁸⁴ Subjects are instructed to walk back and forth, in a **20 m stretch of hallway**, for six minutes, at a pace that would make them tired by the end of the walk; encouragement and feedback are given according to published guidelines. They are allowed to rest during the test if needed, but this time is included in the 6 minutes. Reference equations are available for calculating percent of age- and gender-specific norms.⁸⁵ In community dwelling elderly, measurement error was estimated at 20 meters and this will be used as the threshold value for determining true change. The 6MWT correlates moderately with VO₂max indicating that these two tests measure related but not identical constructs. As daily activity is mostly pursued at a sub-maximal level, functional walking capacity is a more direct measure of capacity for daily routine than a maximal test of exercise capacity such as VO₂max and is more feasible to perform in the perioperative population. The test-retest reliability has been reported to range from 0.73 to 0.99 among a variety of populations, including the elderly. The 6MWT has been shown to be reliable and valid in many populations including surgical ones, with a recent paper supporting its validity as a measure of recovery after colorectal surgery.⁸⁶ The 6 minute walk test will be administered at baseline, after completion of the prehabilitation program, and at 4 and 8 weeks after surgery to assess the impact of the intervention throughout the perioperative period.

- CPET serves as a gold standard and provides assessment of the integrative exercise responses involving the pulmonary, cardiovascular, hematopoietic, neuropsychological, and skeletal muscle systems, which are not adequately reflected through the measurement of individual organ system function.⁸⁷ This non-invasive, dynamic physiological overview permits the evaluation of both submaximal and peak exercise responses, providing the doctor with relevant information for clinical decision making. CPET is increasingly being used in a wide spectrum of clinical applications for the evaluation of undiagnosed exercise intolerance and for the objective determination of functional capacity and impairment. Its use in patient management is increasing with the understanding that resting pulmonary and cardiac function testing cannot reliably predict exercise performance and functional capacity and that overall health status correlates better with exercise tolerance than with resting measurements. CPET parameters (ECG, $\dot{V}O_{2max}$, HF, AT, RQ) will be administered at baseline to establish exercise intensity, after prehabilitation (1 week before surgery), and at 4 weeks after surgery to assess the impact of the intervention.
- Muscle strength
 - Hand grip strength test can be used to characterize general upper extremity muscle strength,^{88,89,90} and can increase after general upper extremity resistance training including exercises that did not specifically involve handgrip strength.⁹¹ Upper extremity muscle strength of adults is measured using a JAMAR grip strength dynamometer.
 - Stair climb test has the time needed to climb a stair as the basic variable. Together with the vertical displacement and body weight, the stair climb power is calculated.⁹² This value is normalized by body weight. The test-retest reliability of the 10-step stair climb power test in a population of elderly people (range 65-94 years) is very high ($r=0.99$).⁹² Leg press power at 40% of 1RM weight showed a correlation of $r=0.47$ ($P<0.001$) with the stair climb power. Leg press power at 70% of 1RM weight showed a correlation of $r=0.52$ ($P<0.001$) with the stair climb power. Climb power in wattage per kg is calculated by the following formula: $\text{body weight(kg)} \times 9.81 \times (\text{height stairs (m)}/\text{time(s)})$.
 - Sit-to-Stand test is a recognized Senior Fitness Test and used to assess an individual's lower-body strength.⁹³ This is done by having the individual sit on a chair and attempt to stand as many times in a maximum of 30 seconds.^{94,95,96}
 - The sit-to-stand test requires a minimum amount of instrumentation. The necessary equipment includes the use of a stopwatch and a standard armless chair. The back of the chair should be placed against a wall to maintain stability and prevention of slipping.⁹⁷ Patients are encouraged to have their arms crossed on their chest during the test to avoid the use of the upper limbs. Patients are instructed to rise from the chair to a full stand on the signal "go" and then return to a fully seated position. The individual is allowed to have at most two practice trials and a demonstration should be given. The demonstration should be done slowly at first to show proper form and another demonstration should be given at a faster pace to show that the objective of the test is to do as many sit to stands one can do in the given amount of time.⁹⁸
- The indirect 1 repetition measures are used to dose the training and will be administered at baseline, on the day before surgery, in the week after discharge from surgery and at 4 and 8 weeks after surgery to assess the impact of the intervention throughout the perioperative period. Muscle groups tested by 1-RM measurements are ⁹⁹ The 1RM is calculated by the Brzycki formula: $1RM=W*36/(37-r)$ (w =weight, r =repetitions).¹⁰⁰
- Nutritional status, including body composition, will be assessed at baseline, after completion of the program and 4 and 8 weeks postoperatively by using the following tools:
 - The Patient-Generated Subjective Global Assessment Short Form (PG-SGA SF) screening tool will be used to identify malnutrition. This is an internationally validated instrument and preferred screening method to identify malnutrition in oncologic patients.^{101,102,103,104,105} A three-day food diary filled in by patients is used to assess protein and calorie intake¹⁰⁸. The energy requirements of the patient are calculated by the Harris-Benedict formula by Rosa.^{106,107} Håkonsen et al recommended the PG-SGA as a nutritional assessment tool in colorectal cancer patients in combination with other parameters.¹⁰⁸ The PG-SGA consists of two parts: 1) the first part is the Patient Generated Subjective Global Assessment Short Form (PG-SGA SF) which includes a brief questionnaire addressing current weight, weight history, acute weight changes, changes in food intake over the past month, occurrence of nutrition impact symptoms experienced over the previous 2 weeks and changes in physical activities and functions over the previous month. The PG-SGA SF will be completed by patients themselves and generates a score for nutrition risk. The PG-SGA SF is a widely validated malnutrition screening tool in cancer patients.¹⁰⁹ 2) The second part will be completed by the dietician and includes a physical examination, where fat and muscle stores an fluid status are assessed, and assessment of the disease/ condition and metabolic demand. The global PG-SGA generates a subjective category rating for nutritional status: well-nourished (PG-SGA A), suspected malnutrition or moderate malnutrition (PG-SGA B), or severe malnutrition (PG-SGA C). It also provides a numeric score used for triaging (nutritional) intervention, i.e. to indicate the need for a calorie enriched diet.
 - Anthropometry. For a first impression of body composition and function, a minimal set of anthropometric measurements are performed. Body weight, length, triceps skinfold, hand grip strength and circumferences of wrist, waist and upper arm are measured. With these measurements, body frame can be determined, and Body Mass Index ($\text{body weight (kg)} / (\text{length})^2$), and muscle- and fat surface area can be calculated. When compared with reference values, one can assess (change in) body weight, (subcutaneous) fat mass, (upper limb) muscle mass and muscle strength, taking into account patients' body frame (S, M, L).¹¹⁰ Measurements will be carried out according to the Anthropometry Procedures Manual of the National Health And Nutrition Survey.¹¹¹

- Body Mass Index will be calculated with the equation body weight (kg)/ body length (cm)². According to the following classification patients' body weight status will be categorized:

- BMI < 18,5 (18-65 years old), BMI < 20 (> 65 years old), BMI < 21 (COPD) underweight
- BMI 18,5/20 or 21(dependent of age/COPD) -24,9 normal weight
- BMI 25 (18-65 years old), BMI 27 (> 65 years old) -30 overweight
- BMI > 30 obesity or severe overweight

- Percentage of body weight loss in the previous 1 and 6 months will be calculated based on the measurement of current body weight and anamnestic required body weight of 1 month or 6 months ago.

- Food diary & 24-hour recall

In the week before start of the training program and in the last week prior to surgery, a three-day food diary will be filled in by the patient and assessed by a registered dietician, to obtain information about patients' food intake. During hospitalization the period (days) of being sober until commencement of oral intake is recorded. At the 5th day of hospital admission, a registered dietician will perform a 24-h recall, to estimate energy and protein intake of the day before and to determine caloric or protein shortage. The energy requirements of the patient are calculated by the Harris-Benedict formula by Roza.^{112, 113}

o Estimated energy requirements

Energy requirements will be estimated using the revised resting energy expenditure (REE) predictive equation of Harris and Benedict,¹¹³ adjusted for relevant stress and activity factors (1,3-1,5).

In a validation study of predictive equations for resting energy expenditure in adult in- and outpatients, Weijs et al¹¹⁴ showed that the revised Harris and Benedict was one of the best predictive equations, also for underweight patients. Total energy expenditure will be calculated by increasing estimated REE with 30-50%, dependent on stress and activity factors.⁵⁷

o Estimated protein requirements

Due to anabolic resistance in elderly patients, higher dietary protein intake is required to obtain positive protein balance and to maintain or increase muscle mass. Also, inflammatory disease such as cancer and physical (strength) training elevate protein requirements. The required amount of protein will be estimated according to the following calculations:

- o 1.5-1.8 gram protein/ kg body weight*, daily**
- o 0.4 gram isolated whey protein/ kg body weight*, within 1 h-post exercise and before sleep

*In case of underweight, protein requirements are underestimated since the body contains more protein/ kg body weight when compared to normal body weight. Opposing, in overweight subjects, protein requirements are overestimated when actual body weight is used in this equation. Therefore, in over- and underweight patients, adjusted body weights will be used in this equation, according to current guidelines for cancer patients.⁵⁷

BMI	Correction
< 20	Adjustment of body weight to a body weight in accordance with a BMI of 20 protein recommendation (grams) x length (m) ² x 20
20-27	Actual body weight
>27	Adjustment of body weight to a body weight in accordance with a BMI of 27 protein recommendation (grams) x length (m) ² x 27

Patients are recommended to use dietary proteins in boluses of 20 grams (70+ years: 25 grams)- 30 grams of dietary protein per meal, since this may increase protein synthesis.

** The safe upper limit for dietary protein intake is unknown. Protein recommendations for high intensity strength training go up to 2.0 gram/ kg body weight.

- Health-related quality of life (HRQL) as measured by the acute (1 week recall period) RAND health survey (19) and the EORTC QLQ-C30 for cancer patients and EORTC QLQ-CR29 specifically for colorectal cancer patients. The RAND is the most widely used HRQL measure and has been validated for surgical population (20). It incorporates behavioral functioning, subjective well-being and perceptions of health by assessing, on a 0 to 100 scale, eight health concepts: (1) Physical function (PF) -limitations in physical activities due to health problems; (2) Role physical (RP)-limitations in role activities due to physical health problems; (3) Role emotional (RE) -limitations in usual role activities due

to emotional problems; (4) Social functioning (SF) –limitations in social activities due to health problems; (5) Bodily pain (BP)-pain; (6) General health (GH) -general health perceptions; (7) Vitality (VT) -energy and fatigue; and (8) Mental health (MH) -general mental health. Two summary scores have been developed: the Physical Component Summary (PCS) and the Mental Component Summary (MCS)), standardized to have a mean of 50 and a standard deviation of 10. A higher score on the RAND sub-scales or component summary measures indicates a better quality of life. A change of as little as two units on the PCS has been shown to be the minimum clinically meaningful change; 5 points is often targeted by medical intervention studies, though surgical interventions can have an impact as large as 10 points. The RAND and EORTC QLQ-CR29 and EORTC QLQ-C30 will be measured at baseline, before surgery, 4 weeks, 8 weeks and 1 year after surgery.

- The vulnerability of older patients will be measured by two different scores, the Fried frailty score and the G8 score. The Fried Frailty Score will be looked at (baseline) to determine whether the patient can be classified as frail based on five different categories such as weight loss, weakness through hand grip, endurance, slowness and activity level.¹¹⁵ The G8 score is an instrument based on 8 different items to identify a geriatric risk profile in patients and has a strong prognostic value for deterioration and survival.¹¹⁶ It has a high sensitivity and negative predictive value to assess the fragility of older patients with cancer who will go for elective abdominal surgery and will be measured at the start of the study.¹¹⁷
- Physical activity level will be measured through an activity questionnaire derived from the Community Health Activities Model Program for Seniors (CHAMPS) questionnaire.¹¹⁸ This questionnaire is a self-reported measure of physical activity, comprising 18 activities evaluated according to the total number of hours done during an average week. Physical activity will be measured at baseline, before surgery, and at 4 and 8 weeks after surgery. More objective levels of physical activity are assessed using an accelerometer, a small and lightweight device, which detects accelerations. Patients in both the intervention and control group will wear the accelerometer for 4 weeks. Although accelerometers may underestimate some activities, such as cycling and water activities, it is recognized as a reasonably valid tool to objectively assess physical activity.^{119,120,121,122} Accelerations are converted into activity counts per minute, indicating the level of physical activity.
- Depression and anxiety will be assessed by the GAD-7 and PHQ-9 questionnaires at baseline, before surgery, and at 4 and 8 weeks after surgery. The GAD-7 is a valid and efficient tool for screening for generalized anxiety disorder (GAD) and assessing its severity in clinical practice and research.¹²³ The PHQ-9 including nine questions, is half the length of many other depression measures, has comparable sensitivity and specificity, and consists of the actual nine criteria on which the diagnosis of DSM-TV depressive disorders is based.¹²⁴
- Compliance with the interventions is assessed by self-report, and attendance and exercise logs filled in by either the physical therapists or kinesiologist and psychologist (e.g. observed attendance at and compliance with the exercise). Non-responders and dropouts receive a short questionnaire to assess the reason for non-participation or dropping out of the study. Satisfaction with intervention after completion of the intervention programs, patients are asked to complete a brief questionnaire addressing the perceived efficacy of and satisfaction with the program, whether they would suggest any changes to the program and if they would recommend it to other patients undergoing similar treatments.
- Costs of the exercise programs, data on health care costs, patient and family costs and costs of production losses are collected using monthly cost diaries measured on a three-monthly basis during the entire follow up period. Health care costs include the costs of oncological care, general practice care and physiotherapy, additional visits to other health care providers, prescription of medication, professional home care and hospitalization. Patient and family costs include out-of-pocket expenses such as travel expenses and costs for paid and unpaid help. Costs related to production losses include work absenteeism for patients (or parents) with paid jobs and days of inactivity for patients (or parents) without a paid job.

Patients will return to the hospital at 4 and 8 weeks to see either the sport physician or physiotherapist/kinesiologist, as well to collect the postoperative data. Questionnaires for PROMs will be additionally performed 1 year post surgery. We will also measure surgical reinterventions, chemotherapy, hospital visits and mortality 1 year postoperatively.

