- Diet and rest: the diet is focused on a protein intake of 1,5-1,8 g/kg/day with 0,4 g/kg/day whey proteins after training and 0,4 g/kg/day casein proteins before bedtime. This is further explained in the nutrition section of the protocol.

With the training program we try to achieve the following improvements:

- Increase of 10% of VO₂-peak
- Increase of 15% of VO₂-peak at AT
- Increase of 20-40% in 1RM tests (or increase in dumbbell weight)
- Increase in the distance of 10% at 6MWT (at <500m)
- Decrease of 10% of the stairs climb test

At baseline, after prehabilitation (1 week before surgery) and 4 weeks after surgery CPET will be performed. At baseline, the week before surgery, 4 and 8 weeks postoperatively, muscle strength will be tested with the sit-to-stand test, 1-RM and handgrip strength. Functional capacity will be tested at the same time points using the 6-minute walk test and stair climb test. Patients in both groups will wear an accelerometer during four weeks before surgery and four weeks after surgery in order to estimate (changes) in physical activity outside of the hospital in the control and intervention group.

Determine AT:

While slowly increasing the resistance, the VO₂, VCO₂ and VE (expired ventilation) will initially rise linear, up to the moment lactic acidosis develops. With effort above the anaerobic threshold (AT) the CO₂ rises faster than the O₂ uptake, because the CO₂ produced from HCO₃⁻, by buffering lactate, is added to the CO₂ production. VE rises with the increase of CO₂ output (isocapnic buffering), there is still a linear relation whereby EQCO₂ (VE/VCO₂) remains constant (or a light decrease), while EQO₂ (VE/VO₂) increases.

- Increase of VE/VO₂, while VE/VCO₂ remains constant (or light decreases).
- Increase of PETO₂ (change in linearity) vs workload.
- V-slope: change in linearity of VO₂ vs VCO₂

Determine RCP:

If the workload (Watt) after AT further increases, VE rises faster than de CO₂ output, i.e. a rise of EQCO₂ (VE/VCO₂), which ensures for a decrease of PaCO₂ and PETCO₂ (hyperventilation). The point at which the VE rises more than needed for the CO₂, and the PETCO₂ decreases is a 'extra' ventilatory response and is also called 'respiratory compensation point' (RCP). The increase of H⁺ concentration stimulates the carotic bodies (vascular glands) to increase the ventilatory drive as a reaction at the lactic acidosis. By an increase of VE the arterial PCO₂ decreases.

- Increase of VE/VCO₂ vs workload

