8.1.2 Secondary study parameters/endpoints (if applicable)

Secondary outcomes include Patient Reported Outcome Measurements (PROMs) such as health related quality of life (HRQoL) (EORTC QLQ-CR29 and EORTC QLQ-C30, RAND questionnaires) and depression and anxiety scores (GAD-7, PHQ-9 questionnaires), functional capacity (VO₂max, sit to stand test, stair climb test, 1-RM, hand grip strength and self-reported physical activity), nutritional status, length of hospital stay, study compliance, and a cost-effectiveness analysis.

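### The stair climb formula is labelled watts per kg, but as printed it returns watts, so body weight stays in the result

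*Protocol*

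**What the plan says.** The stair climb test is a secondary outcome. Section 8.1.2 lists it under "functional capacity (VO₂max, sit to stand test, stair climb test, 1-RM, hand grip strength and self-reported physical activity", and section 9.7 lists it again. Section 5.1 and Appendix I schedule it at baseline, in the week before surgery, and at 4 and 8 weeks after surgery.

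Section 8.3 describes the derivation. Climb time is the basic variable. Then: "Together with the vertical displacement and body weight, the stair climb power is calculated". The next sentence reads: "This value is normalized by body weight". After some reliability and correlation figures the passage continues "Climb power in wattage per kg is calculated by the following formula" and prints the product of body weight (kg), 9.81, and stair height (m) over time (s). The protocol gives no other stair climb equation and no separate equation for the normalizing step.

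**The concern.** The label and the formula describe two different variables. Power per kg depends only on how fast the patient climbs. The printed product depends on climbing speed and on body weight. Someone who programs the equation and someone who programs the label would produce different data from the same measurements.

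Weight is not a neutral nuisance here. The intervention includes tailored energy and protein advice that takes weight loss into account (section 5.1), and the introduction reports malnutrition or unintended weight loss in up to 36.4% of these patients. Randomization balances baseline weight on average, but it does not hold weight after baseline equal between arms. If the arms differed in weight change, the printed formula would show part of that difference as a difference in stair climb power.

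**Working it through.** **Inputs from the protocol (section 8.3).** Printed formula: weight (kg) × 9.81 (m/s²) × height (m) / time (s). Stated unit: watts per kg.

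**Unit check.**
- As printed: kg × m/s² × m/s = kg·m²/s³ = W.
- Divided by weight: 9.81 × height/time, in m²/s³ = W/kg.

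The stated unit is not reproduced. The printed result exceeds the named one by a factor equal to body weight in kg. This does not depend on any assumed value.

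**Illustration.** The protocol gives no stair height, climb times or body weights for this test. Assumed here: height 1.7 m, time 4 to 8 s, weight 60 to 100 kg.

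At 5 s, power per kg is 9.81 × 1.7 / 5 = 3.34 W/kg at every weight. Over the assumed times it runs from 4.17 W/kg (4 s) to 2.08 W/kg (8 s).

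| Weight | Time | Formula as printed (W) | Per kg (W/kg) |
|---|---|---|---|
| 60 kg | 5 s | 200.1 | 3.34 |
| 80 kg | 5 s | 266.8 | 3.34 |
| 100 kg | 5 s | 333.5 | 3.34 |
| 100 kg | 8 s | 208.5 | 2.08 |

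**Between patients.** At equal time the printed value rises in proportion to weight: 100/60 = 1.67, or +67% from 60 to 100 kg. The 100 kg patient who takes 8 s scores above the 60 kg patient who takes 5 s (208.5 against 200.1), although per kg the order is reversed (2.08 against 3.34). The break-even time for the heavier patient is 5 × 100/60 = 8.33 s. Beyond that, the heavier patient scores lower on the printed formula too.

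**Within a patient.** The 5% weight loss is an illustration; the protocol gives no expected figure for the trial.
- 80 kg falling to 76 kg at an unchanged 5 s: the printed value goes from 266.8 to 253.5, that is 76/80 − 1 = −5%. Power per kg stays at 3.34.
- A 10% shorter climb time raises power per kg by 1/0.90 − 1 = 11.1%. Combined with a 5% weight loss, the printed formula shows 0.95/0.90 − 1 = 5.6%, about half.

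These percentages do not depend on the assumed height, time or starting weight.

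**The case against.** The strongest reply is that section 8.3 sets out two steps: first absolute power from time, height and weight, then normalization, which is stated in words. On that reading the printed expression is the first step and only its label has slipped. The intended quantity is indeed clear from the text. The reading still fails as a defence, because the sentence that introduces the expression says that the expression itself yields power per kg. The document contains no second equation.

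The second reply is stronger. A reader might infer that the analysed secondary endpoint is wrong. The documents do not establish that. Sections 8.1.2 and 9.7 name the stair climb test, not stair climb power. Section 8.3 treats time as the basic variable. The training target in section 5.1, "Decrease of 10% of the stairs climb test", fits a time, since improvement would raise power. If time is what is analysed, the formula does not touch the result, and that choice may be made in a statistical analysis plan that is not at hand.

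A reader might also infer that the formula always ranks heavier patients as fitter. It does not: the ranking holds only at equal time, or when the heavier patient is slower by less than the weight ratio. Nor can a definite loss of precision be claimed. The documents give no spread for body weight or stair climb power and no correlation between them, and the mixed model for repeated measurements in section 9.7 could absorb much of the stable difference in weight between patients.

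Finally, the diet in section 5.1 aims at lean mass and nutritional status and sets no weight-gain goal, so the size and direction of any weight difference between arms are unknown.

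**Conclusion.** The contradiction stands. The protocol states a derivation rule that returns watts while calling the result watts per kg and normalized. The discrepancy is exactly a factor of body weight and rests on units alone. Its consequence is conditional: it arises only if stair climb power is analysed and the expression is programmed as printed. In that case a percentage change in weight carries over one for one into the outcome at unchanged climb time.

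The reach is modest. The outcome is secondary, and the primary endpoints, sample size and interim rules are unaffected. The correct value can be recovered for every patient, because Appendix I schedules body weight at each of the four stair climb visits and the climb time is recorded.

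**What to change.** In section 8.3, label the present expression as stair climb power in watts. Add the normalized value as its own equation: power per kg (W/kg) = 9.81 × height (m) / time (s). State that this normalized value is used wherever stair climb power is analysed.

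The cost is a line of protocol text and, where one has been written, the matching line of the derivation program. No new data are needed. Values already derived from the printed formula can be corrected by dividing by the body weight that was used.
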